6.3. Classification

6.3.1. Intensity / Severity

All adverse events should be graded on a 4 point scale (mild, moderate, marked, severe) for intensity / severity. These definitions are as follows:

- **Mild:** Transient discomfort; no medical intervention / therapy required and does not interfere with daily activities.
- **Moderate:** Low level of discomfort or concern with mild to moderate limitation in daily activities; some assistance may be needed; minimal or no medical intervention/therapy required.
- **Marked:** Considerable discomfort with limitation in daily activities; some assistance usually required; medical intervention/therapy usually required.
- **Severe:** Extreme discomfort and limitation in daily activities; significant assistance required; **significant** medical intervention/therapy required.

Note: There is a distinction between the severity and the seriousness of an adverse event. Severity is a measurement of intensity; thus, a severe reaction is not necessarily a serious adverse event (SAE). For example, a headache may be severe in intensity, but would not be serious unless it met one of the criteria for serious adverse events.

6.3.2. Expectedness

All AEs should be evaluated as to whether they are expected or unexpected.

- **Expected (anticipated):** An adverse event is expected when the nature, severity or degree of incidence was previously described.
- **Unexpected (unanticipated):** An adverse event is unexpected when the nature, severity or degree of incidence was not previously described.

6.3.3. Relatedness

The study investigator should evaluate if the AE is related to the use of the study device. Relationship is defined in the following manner:

Not related: Evidence indicates no plausible direct relationship to the study device such that:

- A clinically plausible temporal sequence is inconsistent with the onset of the AE and device application, and/or
- A causal relationship is considered biologically implausible, and/or
- The AE can be attributed to concurrent/underlying illness, other drugs or procedures.

Possibly related: Evidence indicates a possible relationship to the study device such that:

- The event occurs within a reasonable period of time relative to the application that makes a causal relationship possible, but plausible explanations may also be provided by other causes such as other drugs, products, chemicals, underlying disease, environment, etc., and/or
- The event is possibly related to the study application.

Related: Evidence indicates a reasonable temporal sequence of the event with the study device application exists or that the association of the event with study device application is unknown and the event is not reasonably supported by other conditions such that:

- There is a clinically plausible time sequence between onset of the AE and study device application a, and/or
- There is a biologically plausible mechanism for study application causing or contributing to the AE, and/or
- The AE cannot be reasonably attributed to concurrent/underlying illness, other drugs or procedures.

6.3.4. Outcome

The clinical outcome of an AE should be characterized as follows:

- Resolved without sequelae
- Resolved with sequelae (specify)
- Ongoing (i.e. continuing at time of study discontinuation)
- Death

6.3.5. Treatment or Action Taken

The clinical treatment or action taken from an AE should be characterized as follows:

- None
- Medical intervention
- Surgical intervention
- Other

6.4. Anticipated Adverse Events

The following is a list of anticipated adverse events:

- Ocular discomfort or irritation
- Conjunctival injection
- Canaliculitis
- Subconjunctival hemorrhage
- Punctal stenosis
- Eyelid telangiectasia
- Eyelid edema

- Eyelid induration
- Eyelid erythema
- Epiphora
- Clinically significant decrease (>10 letters) in Corrected Distance Visual Acuity
- Clinically significant increase in corneal epithelial staining, e.g., an increase in corneal staining score of 2 or more in at least one corneal region or an increase in the sum for all corneal regions of 4 or more (using NEI grid and scale)

7. INVESTIGATOR QUALIFICATIONS AND RESPONSIBILITIES

7.1. Qualifications

The investigator is a licensed physician who has completed a residency in ophthalmology.

7.2. Responsibilities

The investigator has the following responsibilities:

- Ensure that the clinical study is conducted in accordance with the ethical principles that have their origin in the Declaration of Helsinki, ISO 14155:2011, GCP, ICH guidelines, and any regional or national regulations as appropriate.
- Ensure that participants undergo no investigational procedures other than those described in this protocol and approved by the IRB, except those procedures deemed necessary to protect the health and well-being of the participants. Any such procedures will be documented in the participant's records and reported to the sponsor and the IRB.
- Report any use of the investigational device without first obtaining informed consent to the IRB and sponsor
- Assure that all participants entering the study conform to the participant selection criteria
- Assure that IRB approval of the study protocol and informed consent has been obtained and provided to the site prior to initiation of the study
- Perform the participant evaluations as described in the study protocol and not deviate from the study protocol unless protection of the health, safety or welfare of study participants requires prompt action
- Notify the IRB of unanticipated adverse device effects
- Ensure participant confidentiality

- Submit regular progress reports to the IRB as required
- Report any emergency deviations from the protocol that are necessary to protect study participants to the IRB within five working days of occurrence
- Submit a final report for the study to the IRB in a timely manner
- If any additional requirements are imposed by the IRB or regulatory authority, these requirements shall be followed.

7.3. Informed Consent Process

The site will submit the proposed informed consent to the IRB. Potential participants cannot be asked to sign the informed consent form until the study has been fully approved by the IRB. The following information should be provided in the informed consent:

- The study is research
- Purpose of the study, including the approximate duration of participation by the participant and a description of the procedures
- Possible side effects, risks or discomforts of the investigational device
- Reasonably expected benefits
- The existence of alternative therapy options and/or alternatives to participating in the study
- Confidentiality of records
- Costs and compensation or treatment for injury
- Person to contact regarding participant rights or for questions on research or research-associated injury
- That participation is voluntary
- The right to discontinue participation from the study at any time without disadvantage to the participant
- That the participant will be informed of new information learned during the study, which may affect the participant's decision to continue participation in the study

The investigator will obtain written informed consent from each participant prior to the initiation of any study-specific activities. Copies of the informed consent form used in the study should include the IRB-approved stamp (if applicable) and version date. The participant or participant's legally authorized representative (if applicable) will be allowed sufficient time to thoroughly read, or have read and explained to them, the informed consent form. The investigator will answer any questions that the participant or representative might have. If the participant agrees to participate in the study, all required parties should sign and date the informed consent form. The original signed

informed consent form will be retained by the site and a copy will be given to the participant for his/her records. The obtaining of informed consent and the date of that informed consent should be noted in the participant's medical record. It should also be noted in the participant's medical record that informed consent was obtained prior to conducting any study-specific activities.

7.4. Records

7.4.1. Source Documents

Source documentation for this study will be maintained to document the application and study course of each participant and to substantiate the integrity of the trial data. Source documentation will include, but may not be limited to, worksheets, hospital and/or clinic or office records documenting participant visits including study and other treatments or procedures, medical/ophthalmologic history and physical examination information, laboratory and special assessment results, pharmacy records, device accountability records, and medical consultations. In this study, case report forms can be used as source documents where appropriate.

The investigator is responsible for maintaining adequate case histories in the source documents of each participant. The following data will be reported by the investigator in the source medical records of each participant enrolled in the study:

- The date the participant entered the study and the participant number
- The study protocol number
- The date that informed consent was obtained
- Evidence that the participant met the study eligibility requirements (e.g., medical history, study procedures and/or evaluations)
- The dates of all study-related participant visits
- Evidence that required procedures and/or evaluations were completed
- Use of any concurrent medications
- Occurrence and status of any adverse events
- The date the participant exited the study and a notation as to whether the participant completed the study or was discontinued, including the reason for discontinuation.

7.4.2. Case Report Forms

Case report forms will be filled out completely for each participant in accordance with instructions. The investigator should ensure that all data on the CRF is accurate and consistent with the source documents. Only the principal investigator may sign and date the designated CRF page(s).

7.4.3. Screening/Enrollment Log

The investigator will maintain a screening log that will record the date of screening, the enrollment status (enrolled/excluded), the date of informed consent and the reason for exclusion for all screen failures.

7.4.4. Device Accountability

The investigator will be responsible for maintaining a device accountability log that will track device usage for all study participants. Information tracked will include date of device application, lot number and the participant ID.

7.4.5. Record Retention

The investigator is responsible for maintaining adequate records to enable the conduct of the study to be fully documented. This includes:

- Signed protocol and amendments
- Signed and dated informed consents per institutional policy
- Signed, dated, and completed CRFs and documentation of CRF corrections
- Notification of SAEs and related reports
- All study device dispensing and accountability logs
- Shipping records of investigational device and trial-related materials
- Dated and documented IRB protocol approvals and all correspondence between the investigator and IRB
- *Curriculum vitae* and current medical license for principal investigator

The investigator must maintain a copy of all study documents for the period of time that is required by the regulatory authorities.

7.4.6. Deviations from the Investigational Plan

The investigator shall notify the IRB of any deviation from the Investigational Plan to protect the life or physical well-being of a participant in an emergency. Such notice shall be given as soon as possible, but in no event later than five (5) working days after the emergency occurred.

8. ETHICS

8.1. Study Conduct

The study will be performed in accordance with the relevant parts of the Code of Federal Regulations, ICH Guidelines for Good Clinical Practices, the Declaration of Helsinki and any other applicable regional and/or national regulations.

8.2. Ethics Review

Before any participant can be enrolled in this study, the IRB will review and approve the protocol and the Informed Consent Form to be used.

8.3. Confidentiality

Confidentiality of participants will be maintained throughout the study. A unique identification code will be assigned to each participant enrolled in this study. Any data that may be published in abstracts, scientific journals, or presented at medical meetings will reference a unique code and will not reveal the participant's identity.

8.4. Amendments to the Protocol

Any amendment containing major modifications (particularly if it may involve an increased risk to the participants) must be approved by the IRB before it may be implemented. No change in the conduct of the study will be instituted without written approval from the Sponsor.

9. APPENDICES

9.1. Appendix A – Schedule of Assessments

Procedure/Assessments	Baseline	Application	Form 1	Form 2	Form 3
	Day -30 to 0	Day 0	Day 3 ± 1	Day 14 ± 2	Day 42 ± 5
Informed Consent/HIPAA	X				
Demographics	X				
Eligibility	X				
OSDI Questionnaire (OD, OS separately)	X	X	X	X	X
CDVA	X	X	X	X	X
Slit Lamp Examination	X	X	X	X	X
Grading of Corneal Staining	X				X
Schirmer Test	X				X
Tear break-up time	X				X
Tear meniscus height	X				X
Application of device and control		X			
Removal of device					X
Adverse Events		X	X	X	X

9.2. Appendix B – Examinations and Procedures

9.2.1. Questionnaire

To minimize bias, participants will be asked to complete the questionnaire independently and in private after instructions have been provided by site personnel. The questionnaire should be completed twice and answered by the participant with reference to each eye individually.

Ocular Surface Disease Index (OSDI)

The OSDI is a 12-item questionnaire generated by the Outcomes Research Group at Allergan (Irvine, CA),¹⁴ which asks participants to describe the severity and the nature of their irritation symptoms. The participant will answer the 12 questions by circling the number that best represents each answer: 4 (all of the time), 3 (most of the time), 2 (half of the time), 1 (some of the time), or 0 (none of the time). The final score for the questionnaire is calculated as follows:

Add subtotals from Sections I, II, and III = A

Determine total number of questions answered from Sections I, II, and III (do not include N/A) = B

Final OSDI score = A x 25 divided by B

An example of the questionnaire is as follows:

Ocular Surface Disease Index® (OSDI®)²

Ask your patients the following 12 questions, and circle the number in the box that best represents each answer. Then, fill in boxes A, B, C, D, and E according to the instructions beside each.

Have you experienced any of the following during the last week?	All of the time	Most of the time	Half of the time	Some of the time	None of the time
1. Eyes that are sensitive to light? ...	4	3	2	1	0
2. Eyes that feel gritty?	4	3	2	1	0
3. Painful or sore eyes?	4	3	2	1	0
4. Blurred vision?	4	3	2	1	0
5. Poor vision?	4	3	2	1	0

Subtotal score for answers 1 to 5

(A)

Have problems with your eyes limited you in performing any of the following during the last week?	All of the time	Most of the time	Half of the time	Some of the time	None of the time	N/A
6. Reading?.....	4	3	2	1	0	N/A
7. Driving at night?	4	3	2	1	0	N/A
8. Working with a computer or bank machine (ATM)?.....	4	3	2	1	0	N/A
9. Watching TV?	4	3	2	1	0	N/A

Subtotal score for answers 6 to 9

(B)

Have your eyes felt uncomfortable in any of the following situations during the last week?	All of the time	Most of the time	Half of the time	Some of the time	None of the time	N/A
10. Windy conditions?.....	4	3	2	1	0	N/A
11. Places or areas with low humidity (very dry)?	4	3	2	1	0	N/A
12. Areas that are air conditioned?...	4	3	2	1	0	N/A

Subtotal score for answers 10 to 12

(C)

Add subtotals A, B, and C to obtain D
(D = sum of scores for all questions answered)

(D)

Total number of questions answered
(do not include questions answered N/A)

(E)

[figure not shown]
Please turn over the questionnaire to calculate the patient's final OSDI® score.

Evaluating the OSDI® Score¹

The OSDI® is assessed on a scale of 0 to 100, with higher scores representing greater disability. The index demonstrates sensitivity and specificity in distinguishing between normal subjects and patients with dry eye disease. The OSDI® is a valid and reliable instrument for measuring dry eye disease (normal, mild to moderate, and severe) and effect on vision-related function.

Assessing Your Patient's Dry Eye Disease^{1,2}

Use your answers D and E from side 1 to compare the sum of scores for all questions answered (D) and the number of questions answered (E) with the chart below.* Find where your patient's score would fall. Match the corresponding shade of red to the key below to determine whether your patient's score indicates normal, mild, moderate, or severe dry eye disease.

1. Data on file, Allergan, Inc.

9.2.2. Corrected Distance Visual Acuity

Corrected distance visual acuity (CDVA) should be recorded with the participant's current spectacle correction or with the most current spectacle correction in a trial frame using the Early Treatment Diabetic Retinopathy Study (ETDRS) chart. The number of letters read correctly will be recorded. The CDVA should be collected at the screening examination and on the application day, both before and after the three randomized applications are administered, using the same spectacle correction used during the screening examination. If the CDVA is not believed to be maximal during the screening visit, pinhole visual

acuity should be recorded for this reading throughout the study or a manifest refraction should be performed.

Note: Repeated use of topical anesthetic and Schirmer testing may result in a transient decrease in CDVA.

Early Treatment Diabetic Retinopathy Study (ETDRS) Corrected Distance Visual Acuity

The equipment used will include a set of two Lighthouse Distance Visual Acuity Test charts (ETDRS Charts 1 and 2; Lighthouse Low Vision Products Precision Vision, Long Island, New York) and a retroilluminated box providing standardized chart illumination. Most of the room lights should be turned off during the visual acuity test as the box itself provides sufficient illumination for the examiner to record the test results. Additional light can have an adverse effect. With the box light off, not more than 15 foot-candles of light should fall on the center of the chart. A distance of exactly 4 meters is required between the participant's eyes and the visual acuity chart for the 4-meter test and a distance of exactly 1 meter is required for the 1-meter test.

The participant can be standing or sitting and will be asked to focus on an ETDRS visual acuity chart. Testing of all eyes should begin at the 4 meter test distance. The examiner should ensure that the head does not move forward or backward during testing. After careful instruction, testing should begin with the right eye using Chart 1.

The participant should be told (and reminded if appropriate) that the chart has letters only and no numbers. The participant should be asked to read at a steady pace, at a rate no faster than about one letter per second, and not to proceed until providing a definitive response. Examiners should not point to specific letters on the chart or read any of the letters during testing. If the participant says s/he cannot read a letter, s/he should be encouraged to guess. If the participant identifies a letter as one of two or more letters, s/he should be asked to choose one letter. When it becomes evident that no further meaningful readings can be made despite encouragements to read or guess, the examiner should stop the test for that eye.

Each letter is scored as right or wrong. Once a participant has identified a letter with a definite single-letter response and has read the next letter, a correction of the previous letter should not be accepted. If the participant changes a response aloud (e.g. "That was a 'C,' not an 'O') before s/he has read the next letter aloud, then the change should be accepted. If the participant changes a response after beginning to read the next letter, the change is not accepted. The test is repeated for the left eye using Chart 2. Chart 1 should not be exposed to the left eye and Chart 2 should not be exposed to the right eye, even when switching charts and occlusion.

1-Meter Test

Eyes reading 19 or fewer letters correctly at 4 meters should be tested at 1 meter. If the spectacles or trial frame is to be removed when changing the test distance

from 4 meters to 1 meter, the testing chart should first be removed from view to prevent the participant from reading the chart with the fellow eye. Before testing at 1 meter, a +0.75 D sphere should be added to the 4-meter correction already in the trial frame to compensate for the closer testing distance. The avoidance of any head movement forward to backward is particularly important during the 1-meter test. The participant should be asked to read only the first six lines at 1 meter, making 30 the maximum score attainable at that distance.

Light Perception

If visual acuity is so poor that the participant cannot read any of the largest letters at 1 meter (i.e., the number of letters read correctly at 1 meter is zero), light perception should be tested with an indirect ophthalmoscope in a darkened room. The indirect ophthalmoscope light should be in focus at 3 feet with the rheostat set at maximum voltage. From a distance of 3 feet, the beam should be directed in and out of the eye at least four times and the participant should be asked to respond when s/he sees the light. If the examiner is convinced that the participant perceives the light, vision should be recorded as “light perception,” and, if not, vision should be recorded as “no light perception.”

Corrected Distance Visual Acuity Scoring Instructions

The ETDRS visual acuity worksheets are for clinic use only. The examiner records each letter identified correctly by circling the corresponding letter on the appropriate worksheet. The examiner records letters read incorrectly with an ‘X’ and leaves letters for which the participant makes no guesses unmarked. Each letter read correctly is scored as one point. After testing is completed, the score for each line (which is zero if no letters are read correctly) and the total score for each eye are recorded on the visual acuity worksheet. If testing at 1 meter is not required, 30 points are automatically scored for the 1-meter test. The total combined score (i.e., the sum of the 4- and 1-meter scores) are entered on the worksheet as the final visual acuity letter score.

Note: A clinically significant visual acuity decrease (defined as an increase of 0.22 or greater in logMAR score from Day 0) at a Follow-up visit will be considered an adverse event.

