3. STUDY DESIGN

3.1. Description of Study Design

The study is a single-arm, single-center, randomized, single-masked prospective study to evaluate Restylane-Defyne for canalicular occlusion in participants with mild to moderate dry eye disease.

Each participant will have a Screening Visit to determine eligibility. Prior to performing any testing specifically for the Screening Visit, participants will be provided with an IRB approved informed consent form and be given the chance to review and ask questions before written informed consent is obtained. The Screening Visit should occur within 30 days prior to application of the HA gel on Study Day 0 and may occur on Day 0. Participants that meet all eligibility criteria will be invited to participate in the study.

Participants that return or are present for Study Day 0 will be enrolled in the study and will receive the device. Participants will be followed for 42 days and will be seen for follow-up exams at 3, 14 and 42 days.

Participants may continue to use their artificial tears. The use of artificial tears will be recorded.

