3.3.1. Inclusion Criteria

To be eligible for the study, potential participants must meet all of the following inclusion criteria at the Screening Visit:

- Twenty-one (21) to 80 years of age
- Baseline OSDI score of at least 13 with no more than 3 responses of “not applicable”
- In both eyes, a baseline Schirmer test with anesthetic of \leq 10 mm/5 minutes
- Literate, able to speak English and able to complete the questionnaire independently
- Willing to sign the informed consent and deemed capable of complying with the requirements of the study protocol.

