3.8.1. Screening (Day -30 to 0)

Any tests or procedures that are performed to confirm eligibility and are not standard of care must be performed AFTER the potential participant has signed the Informed Consent Form.

The following procedures are performed at the Screening visit:

- Obtain medical history and confirm potential participant's age
- Obtain written informed consent
- Perform urine pregnancy test for women of childbearing age
- Have potential participant complete the Ocular Surface Disease Index (OSDI) for each eye individually
- Perform Corrected Distance Visual Acuity
- Perform baseline TBUT test
- Perform baseline tear meniscus height test
- Administer fluorescein stain
- Perform slit-lamp biomicroscopy and assess corneal staining using the NEI grid and scoring system
- Perform baseline Schirmer test with topical anesthetic

If at any point in this process, the potential participant fails to meet eligibility, the process should be discontinued, and the potential participant should be recorded as a screen failure along with the reason.

3.8.2. Day 0

The following procedures are performed at the Day 0 visit:

- Have participant complete the OSDI for each eye individually
- Perform Corrected Distance Visual Acuity
- Instill HA device in inferior canaliculus of eye randomized to the device
- Instill saline in inferior canaliculus of fellow eye

3.8.3. Day 3 and 14

The following procedures are performed at the intermediate follow-up visits, Days 3 and 14:

- Have participant complete the OSDI for each eye individually
- Perform corrected distance visual acuity
- Perform slit-lamp biomicroscopy

3.8.4. Day 42

The following procedures are performed at the Day 30 visit:

- Have participant complete the Ocular Surface Disease Index (OSDI) for each eye individually
- Perform Corrected Distance Visual Acuity
- Perform TBUT test
- Perform tear meniscus height test
- Administer fluorescein stain
- Perform slit-lamp biomicroscopy and assess corneal staining using the NEI grid and scoring system
- Perform Schirmer test with topical anesthetic
- Remove device from inferior canaliculus by irrigation (if necessary for complete removal, hyaluronidase may be used)

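### The acuity-loss flag is measured from an unspecified Day 0 reading; for participants screened that day this reading can follow anesthetic and Schirmer testing, which biases the flag toward missing losses

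*Protocol*

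**What the plan says.** The rule that turns a fall in corrected distance visual acuity (CDVA) into an adverse event is a note at the end of Protocol 9.2.2. The event is "A clinically significant visual acuity decrease (defined as an increase of 0.22 or greater in logMAR score from Day 0) at a Follow-up visit".

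Four other parts of the protocol bear on that reference.

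- **Several readings.** 9.2.2 also states: "The CDVA should be collected at the screening examination and on the application day, both before and after the three randomized applications are administered". Section 3.8.2 lists one Day 0 reading, before instillation. The Schedule of Assessments (Appendix A) has separate CDVA entries for the baseline and application columns.
- **Same-day Screening.** Section 3.1: "The Screening Visit should occur within 30 days prior to application of the HA gel on Study Day 0 and may occur on Day 0".
- **What Screening contains.** In 3.8.1, CDVA comes early in the list and the last item is "Perform baseline Schirmer test with topical anesthetic". The Schirmer result is an inclusion criterion (3.3.1: "In both eyes, a baseline Schirmer test with anesthetic of" at most 10 mm in 5 minutes; the synopsis asks for it in the study eye).
- **The protocol's own warning.** 9.2.2: "Repeated use of topical anesthetic and Schirmer testing may result in a transient decrease in CDVA". It gives neither size nor duration.

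Section 6.4 lists a fall of more than 10 letters as an anticipated adverse event, and 4.7 summarizes acuity changes of more than two lines (11 or more letters). Neither names the CDVA reading from which change is counted.

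**The concern.** A change-from-reference flag is only as good as its reference. If the reference is temporarily low and the later readings are not, every later loss looks smaller than it is. The error does not average out: it always works against detecting harm.

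Here the stated reference is open in two ways. 'Day 0' can mean the reading before application or the one after it. For a participant screened on Day 0, even the reading before application comes after anesthetic and Schirmer testing. The Screening CDVA, taken earlier that day, would avoid both problems, but the rule does not point to it.

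CDVA is a named additional safety assessment. With at most 13 participants, one event that is missed or flagged moves a reported proportion by 1/13, about 8 percentage points.

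**Working it through.** **Step 1. Reproduce the threshold in letters.** Section 9.2.2 gives 30 letters over six lines at 1 meter, so 30 / 6 = 5 letters per line. Assume 0.1 logMAR per line, which the protocol does not state. One letter is then 0.1 / 5 = 0.02 logMAR, and 0.22 / 0.02 = 11 letters. This agrees with 6.4 (more than 10 letters) and 4.7 (11 or more letters). The threshold is consistent across the three sections; only the reference is in question.

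**Step 2. Order of events for a same-day participant.** Eligibility needs the Schirmer result, so anesthetic and strip come before the participant moves on to Day 0 procedures. This does not depend on reading the bullets in 3.8.1 as a time sequence. The application-day CDVA is a separate reading and therefore follows the Schirmer test. No recovery interval is set.

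**Step 3. Follow-up readings.** Days 3 and 14 (3.8.3) include neither anesthetic nor Schirmer. At Day 42 (3.8.4) CDVA is listed before both. The Day 42 statement rests on list order; the Day 3 and Day 14 statement does not.

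**Step 4. Effect on the flag.** Let T be the letter score without any test effect, d the letters by which the reference is lowered, and L the true loss at follow-up.

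- Reference = T − d
- Follow-up = T − L
- Apparent loss = (T − d) − (T − L) = L − d
- Flag if L − d ≥ 11, that is, if L ≥ 11 + d

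The values of d below are assumptions.

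| d (letters) | Apparent size of a true 11-letter loss | Smallest true loss flagged | True losses not flagged |
|---|---|---|---|
| 0 | 11 | 11 | none |
| 1 | 10 | 12 | 11 |
| 2 | 9 | 13 | 11 to 12 |
| 3 | 8 | 14 | 11 to 13 |
| 5 | 6 | 16 | 11 to 15 |

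At d = 5 the effective threshold is 16 × 0.02 = 0.32 logMAR, and a three-line (15-letter) loss would not trip the flag.

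**Step 5. Gains, conditionally.** If the categories in 4.7 were computed from the same reference, the apparent gain would be the true gain plus d. At d = 5, a true gain of 11 − 5 = 6 letters would then count as more than two lines.

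**The case against.** The strongest reply is that the causal step is thin. The note in 9.2.2 speaks of repeated use, while a same-day participant has one Schirmer session. The note also stands in a section that refers to three applications, although this study describes one device and one sham instillation. So the protocol does not say that a single Schirmer test lowers acuity, and d may be 0. It says nothing about fluorescein in this respect. This stands, and the point claims only that losses can be missed.

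Second, when Screening is on Day 0 the Screening CDVA is itself a Day 0 reading, so the wording does not exclude it. That is true, but nothing directs a site to use it, and 3.8, 9.2.2 and Appendix A all treat the application-day reading as separate. The reply confirms that the reference is not fixed.

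Third, bullet order is not a dependable time order: 3.8.1 lists medical history before consent, and break-up time before meniscus height although Appendix B advises the reverse. This weakens the Day 42 part, but not the Day 0 sequence, which follows from eligibility.

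Fourth, a reader might infer that a true loss would go unrecorded. The documents do not support that. CDVA is recorded at every visit, 6.2 requires all adverse events to be documented, and 6.4 is not tied to Day 0. What can fail is the automatic flag.

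Fifth, a reader might infer that all 13 participants are exposed. Thirteen is only the ceiling: 3.5 describes participants as returning for Day 0, and no section says how many will be screened the same day.

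**Conclusion.** The concern holds in a limited form. The acuity-loss flag uses a reference that is ambiguous between readings before and after application. For same-day participants, the reading before application can be lowered by testing that follow-up readings, as listed, do not share. Any such lowering biases the flag toward missing losses.

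Its size is a rise in the effective threshold from 11 to 11 + d letters. This rests on an assumed 0.1 logMAR per line and on an unknown d: over an assumed 0 to 5 letters the threshold runs from 11 to 16, and at d = 0 there is no effect. It concerns between 0 and 13 participants.

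It would go too far to conclude that the 4.7 summary is biased as written. That section names no CDVA reference, and a statistical analysis plan that is not shown may set one. This is a modest correction to a safety rule in a pilot study, worth making because a cleaner reading is already collected.

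**What to change.** In 9.2.2, replace 'from Day 0' with 'from the last CDVA taken before application and before any same-day anesthetic or Schirmer testing'. This is the Screening CDVA when Screening and Day 0 coincide, and otherwise the Day 0 reading before application. Refer to the same reading in the 6.4 item on a fall of more than 10 letters and in the CDVA categories of 4.7, so that all three count change from one place.

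The cost is one sentence and two cross-references. The thresholds stay as they are and no measurement is added. The observed loss rate may come out slightly less favourable.
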